8.5.9 EXPLORATORY ANALYSES

8.5.9.1 Efficacy

Phase 3 segment

The exploratory efficacy endpoints will be analyzed in the same manner as the primary hypothesis, but with a 95% CI and without the hypothesis test p-value.

8.5.9.2 Immunogenicity

Phase 2 segment

Post-baseline increases from baseline in cellular response magnitudes will be compared between treatment groups using differences in medians and associated non-parametric 95% CIs.

The summaries listed above will be stratified according to NP positive/negative status and according to prior receipt of any non-study prophylactic COVID-19 vaccine of the subjects.

Valid samples for statistical analysis purposes will be those collected: at least 6 and no more than 30 days after Dose 2 for the Week 6 timepoint; at least 174 and no more than 198 days after Dose 2 for the Week 30 timepoint; and at least 356 and no more than 380 days after Dose 2 for the Week 56 timepoint. Baseline is defined as the last measurement prior to the first treatment administration.

The PP population will be used for immunogenicity analyses.

Phase 3 Segment

Post-baseline increases in antibody titers from ELISA will be compared between treatment groups using ratios of geometric mean fold-rises and associated 95% t-distribution based CIs.

Post-baseline increases from baseline in cellular response magnitudes will be compared between treatment groups using differences in medians and associated non-parametric 95% CIs.

Post-baseline increases from baseline in neutralizing antibody response titers will be compared between treatment groups using ratios of geometric mean fold-rises and associated t-distribution based 95% CIs.

The summaries listed above will be stratified according to disease status of the subjects.

Valid samples for statistical analysis purposes will be those collected: at least 6 and no more than 30 days after Dose 2 for the Week 6 timepoint; at least 174 and no more than 198 days after Dose 2 for the Week 30 timepoint; and at least 356 and no more than 380 days after Dose 2 for the Week 56 timepoint. Baseline is defined as the last measurement prior to the first treatment administration.

The PP population will be used for immunogenicity analyses.

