In the Phase 3 segment, approximately 6714 seronegative and 402 seropositive subjects 18 years of age and older will be randomized at a 2:1 ratio to receive either active investigational product (INO-4800, 2.0 mg) or placebo (placebo for INO-4800). See Table 2 and Figure 1. Approximately half of seronegative subjects and approximately half of seropositive subjects will be 18-50 years of age, and the other half will be \geq 51 years of age as is operationally feasible. Also, approximately 711 subjects will be \geq 65 years of age, if operationally feasible.

Subjects will be randomized in a stratified manner according to (a) age category (18-50 years vs. ≥51 years) on Day 0, and (b) presence or absence on Day 0 of any of the following underlying medical conditions that increase risk of severe COVID-19 disease, per U.S. Center for Disease Control (CDC) criteria [1], as listed below:

- Cancer
- Chronic kidney disease
- Chronic lung diseases, including Chronic obstructive pulmonary disease (COPD), asthma (moderate-to-severe), interstitial lung disease, cystic fibrosis, pulmonary hypertension
- Neurologic conditions including stroke or cerebrovascular disease that do not impact cognition
- Diabetes (type 1 or type 2)
- Hypertension
- Heart conditions, such as heart failure, coronary artery disease, or cardiomyopathies
- HIV infection (CD4 count >200 cells/mm3 or undetectable viral load)
- Liver disease
- Obesity (BMI ≥ 30 kg/m2)
- Sickle cell disease or thalassemia, or
- Smoking (current or former smoker).

[figure not shown]
Table 2: Phase 3 Segment									
Treatment Arm	Sero status	Expected Number of Subjects	Expo Num Subje	orox. ected ber of ects by Group	Dosing Days	Number of Injections + EP per Dosing Visit	INO-4800 (mg) per injection	INO-4800 (mg) per Dosing Visit	Total Dose of INO-4800 (mg)
			18-50	51+ ^a		2 conig their			(9)
INO-4800	Seroneg	4476	2238	2238	0, 28	2	1.0	2.0	4.0
	Seropos	268	134	134					
Placebo	Seroneg	2238	1119	1119	0, 28	2	0	0	0
	Seropos	134	67	67					
Tatal	Seroneg	6714	3357	3357					
Total	Seropos	402	201	201					
Total		7116			-				

^aat least 711 subjects will be ≥65 years of age

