3.6 EXPLORATORY ENDPOINTS

Table 8: Exploratory Objectives and Associated Endpoints

Pł	Phase 2 Exploratory Objective Phase 2 Exploratory Endpoints	
1.	Evaluate the expanded immunological profile of antibody	 Antigen-specific cellular immune response measured by flow cytometry.
	response and T cell immune response	1b. Expanded immunological profile which may include additional assessments of T and B cell numbers and molecular changes by measuring immunologic proteins and mRNA levels of genes of interest as determined by sample availability
Pł	nase 3 Exploratory Objective	Phase 3 Exploratory Endpoints
1.	Evaluate the efficacy of INO-4800 in the prevention of COVID-19 disease from SARS-CoV-2 variants in subjects who are SARS-CoV-2 seronegative at baseline	 Incidence of virologically-confirmed COVID-19 disease from a SARS-CoV-2 variant starting 14 days after completion of the 2-dose regimen until 12 months post-dose 2 (End of Study (EOS)) in subjects who are SARS-CoV-2 seronegative at baseline
2.	Evaluate the efficacy of INO-4800 in the prevention of SARS-CoV-2 asymptomatic infection in subjects who are SARS-CoV-2 seronegative at baseline	2. Incidence of SARS-CoV-2 asymptomatic infections in SARS-CoV-2 seronegative subjects starting 14 days after completion of the 2-dose regimen until EOS
3.	Evaluate the immunological profile by assessing both antibody response and T cell immune response	 3a. SARS-CoV-2 Spike glycoprotein antigen- specific binding antibody levels 3b. Antigen-specific cellular immune response measured by flow cytometry
4.	Evaluate antibody persistence	 4a. SARS-CoV-2 Spike glycoprotein antigen specific binding antibody levels at Week 30 or later. 4b. Neutralizing antibody response measured by a pseudovirus-based neutralization assay at Week 30 or later

INO-4800	COVID19-311
Inovio Pharmaceuticals, Inc.	Clinical Protocol

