4.2.2 PHASE 3 SEGMENT

- Acute febrile illness with temperature ≥100.4°F (38.0°C) or acute onset of upper or lower respiratory tract symptoms (e.g., cough, shortness of breath, sore throat) on Day 0 prior to dosing;
- Positive serologic test for SARS-CoV-2 at Screening (after approximately 402 subjects positive for SARS-CoV-2 serologic test are randomized, this criterion will apply to all remaining subjects);
- c. Pregnant or breastfeeding, or intending to become pregnant or intending to father children starting from the Screening visit until the last dose;
- d. Positive urine pregnancy test during screening or immediately prior to dosing;
- e. Known history of uncontrolled HIV based on a CD4 count less than 200 cells/mm³ or a detectable viral load within 3 months prior to screening;
- f. Is currently participating or has participated in a study with an investigational product within 30 days prior to Day 0 (documented receipt of placebo in a previous trial would be permissible for trial eligibility);
- g. Previous or planned receipt of an investigational (including Emergency Use Authorization (EUA) or local equivalent authorization) or licensed vaccine for prevention or treatment of COVID-19, MERS or SARS (documented receipt of placebo in previous trial would be permissible for trial eligibility);
- h. Immunosuppression as a result of underlying illness or treatment including:
 - Primary immunodeficiencies (conditions including hypothyroidism, Hashimoto's thyroiditis and vitiligo are allowed);
 - Long term use (≥7 days) of oral or parenteral glucocorticoids at a dose of ≥20 mg/day of prednisone equivalent (use of inhaled, topical, nasal, otic, and ophthalmic corticosteroids are allowed) in the past 6 months;
 - Current or anticipated use of disease modifying doses of systemic anti-rheumatic drugs (e.g., azathioprine, cyclophosphamide, cyclosporine, methotrexate) and biologic disease modifying drugs such as TNF-α inhibitors (e.g., infliximab, adalimumab or etanercept) or others;
 - History of solid organ or bone marrow transplantation;
 - History of or current receipt of any other clinically significant immunosuppressive drugs
 - Diagnosis of an autoimmune disease that may jeopardize the safety of the subject or require therapy that would interfere with study assessments or endpoint evaluation, or otherwise impact the validity of the study results.

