Subjects who require medical care for COVID-19 (or any other suspected condition) will be referred to their primary health care provider or a medical treatment facility if the Investigator believes that the subject should be managed beyond routine care that can be provided by the study site. Subjects referred for treatment will continue study follow-up according to the protocol schedule. If subjects are treated or hospitalized due to their illness, the study team will request COVID-19 specific test results, treatments, treatment outcomes and diagnostics from medical treatment facilities with the subject's written permission. These results and diagnostics will be recorded in the study and/or safety database consistent with protocol reporting requirements.

6.5 **IMMUNOGENICITY ASSESSMENTS**

Whole blood and serum samples will be obtained at visits specified in the Schedule of Events (Tables 3 and 4) for cellular and humoral immunology assessments. Binding ELISA will be evaluated at serial timepoints. Cellular sampling requires 32 mL of whole blood be collected at each visit. Humoral sampling requires collection of 8.5 mL of whole blood in a single 10-mL red top serum collection tube to produce two serum aliquots of 2 mL each. However, baseline (Day 0) immunology samples are required to serve as a baseline for all subsequent immunology testing. Therefore, a total of 68 mL whole blood for cellular sampling and 8 mL serum for humoral sampling is required on Day 0 prior to 1st dose. Subjects may be asked to return for additional blood draws if collected blood sample is lost or unevaluable for any reason. Details of the immunology sample collection and shipment information will be provided in the Laboratory Manual.

Humoral samples will be collected on all subjects and cellular samples will be collected at selected sites (from approximately 711 subjects). Both humoral and cellular analysis will be conducted in the first 102 subjects age 18-50 and in the first 102 subjects age 51 and older enrolled at the sites that are selected for cellular sample collection. In addition, cellular and humoral samples will be analyzed on all subjects with COVID-19 when samples are available.

The immune responses to INO-4800 will be measured using assays that include a pseudovirus-based neutralization assay and ELISpot. Determination of additional analyses using assays not specified, such as assessment of immunological gene

Protocol Version: 2.0USA

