8.5.2.2 Immunogenicity

Phase 3 Segment

Post-baseline increases from baseline in interferon- γ ELISpot response magnitudes will be compared between treatment groups using differences in medians and associated non-parametric 95% CIs.

Post-baseline increases from baseline in neutralizing antibody response titers will be compared between treatment groups using ratios of geometric mean fold-rises and associated t-distribution based 95% CIs.

The summaries listed above will be stratified according to disease status of the subjects and by baseline SARS-CoV-2 serostatus.

Valid samples for statistical analysis purposes will be those collected: at least 6 and no more than 30 days after Dose 2 for the Week 6 timepoint; at least 174 and no more than 198 days after Dose 2 for the Week 30 timepoint; and at least 356 and no more than 380 days after Dose 2 for the Week 56 timepoint. Baseline is defined as the last measurement prior to the first treatment administration.

The PP population will be used for these immunogenicity analyses.

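### The Phase 3 exploratory immunogenicity summaries omit the baseline-serostatus split used for the secondary ones, so binding-antibody and non-ELISpot cellular estimates depend partly on the serostatus mix

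*Protocol*

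**What the plan says.** Section 8.5.9.2 (Phase 3) plans three exploratory comparisons between arms. For binding antibody, "Post-baseline increases in antibody titers from ELISA will be compared between treatment groups using ratios of geometric mean fold-rises". Cellular response is compared by differences in medians, and neutralising antibody by ratios of geometric mean fold-rises. On the analysis set: "The PP population will be used for immunogenicity analyses". On stratification: "The summaries listed above will be stratified according to disease status of the subjects".

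Section 8.5.2.2 covers the secondary Phase 3 analyses of ELISpot and neutralising antibody, with the same methods, population and sample windows (Weeks 6, 30 and 56). Its stratification sentence goes further: "The summaries listed above will be stratified according to disease status of the subjects and by baseline SARS-CoV-2 serostatus".

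Both serogroups are in Phase 3. According to the synopsis, "approximately 6714 seronegative and 402 seropositive subjects 18 years of age and older will be randomized at a 2:1 ratio". Exploratory objectives 1 and 2 in Table 8 are limited to baseline-seronegative subjects. Objective 3 is not: "Evaluate the immunological profile by assessing both antibody response and T cell immune response". Nor is objective 4, on antibody persistence.

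Section 6.5 defines who is assayed: "Both humoral and cellular analysis will be conducted in the first 102 subjects age 18-50", the same number aged 51 and older at the sites chosen for cellular sampling, and subjects with COVID-19 where samples exist.

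**The concern.** Section 8.5.2.2 names disease status and baseline serostatus as two separate factors, so disease status alone in 8.5.9.2 cannot be read as covering serostatus. The exploratory sentence is also out of line with the rest of Section 8. Phase 3 adverse events, vital signs, disposition, demographics, prior medications and concomitant medications are all also presented by baseline serostatus. The Phase 2 half of 8.5.9.2 itself splits by nucleocapsid status. The omission falls on immune responses, where prior infection could plausibly matter most.

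Two things follow. First, ELISA binding antibody, its persistence at Week 30 or later, and cellular responses other than ELISpot would have no planned serostatus-specific summary. If the vaccine effect differs between naive and previously infected subjects, the pooled figure describes neither group. Second, the neutralising comparison is specified twice with different stratification, so the protocol gives two layouts for one analysis.

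The mix is not controlled where it matters. Seropositive subjects are admitted until the exclusion criterion in Section 4.2.2 takes effect ("after approximately 402 subjects positive for SARS-CoV-2 serologic test are randomized"). No corresponding limit is set for the first 102 subjects per age group, and serostatus is not a randomisation factor (Section 8.7).

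**Working it through.** The protocol gives no expected ratio, power or sample size for this comparison, so there is no planned figure to reproduce. The inputs can be checked.

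**Inputs from the protocol**
- Planned seropositive share: 402 / (6714 + 402) = 402 / 7116 = 5.65%.
- Assayed subset: 102 + 102 = 204, before adding COVID-19 cases. If it mirrors the trial, 204 × 0.0565 = 11.5 seropositive subjects are expected (binomial 95% range 6 to 18).
- Binding fold-rise at 2.0 mg in Phase 2, all ages: 23.5 (Section 1.3.7.1). The quoted titres agree closely: 2210.0 / 93.5 = 23.6. Phase 2 excluded subjects with positive serology at screening, so this serves as the seronegative value.
- Neutralising fold-rise at 2.0 mg in Phase 2, all ages: 4.3 (Section 1.3.7.2).

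**Assumptions not in the protocol**
- The placebo fold-rise is 1 in both serogroups.
- The vaccine-to-placebo ratio in seropositive subjects, R_pos, lies between 1 and 10.

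**Formula.** Let s be the seropositive share, equal in expectation in the two arms because of randomisation. The mean log fold-rise in each arm is a share-weighted average over serogroups. Subtracting placebo from vaccine gives

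ln R_pooled = (1 − s) ln R_neg + s ln R_pos.

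**Binding antibody at the planned share.** ln 23.5 = 3.157, and 0.9435 × 3.157 = 2.979.
- R_pos = 1: exp(2.979) gives 19.66, and 19.66 / 23.5 = 0.837, about 16% lower.
- R_pos = 10: exp(2.979 + 0.0565 × 2.303) gives 22.39, and 22.39 / 23.5 = 0.953, about 5% lower.

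The pooled binding ratio over a range of shares, against 23.5 when split, is:

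| Seropositive share | R_pos = 1 | R_pos = 2 | R_pos = 4 | R_pos = 10 |
|---|---|---|---|---|
| 5.65% (planned) | 19.66 | 20.45 | 21.26 | 22.39 |
| 10% (hypothetical) | 17.14 | 18.37 | 19.69 | 21.58 |
| 25% (hypothetical) | 10.67 | 12.69 | 15.09 | 18.98 |
| 50% (hypothetical) | 4.85 | 6.86 | 9.70 | 15.33 |

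**Neutralising antibody at the planned share.** The same formula with R_neg = 4.3 gives 3.96 (R_pos = 1) to 4.51 (R_pos = 10), or −8% to +5%. Section 8.5.2.2 already provides the split result here.

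**No vaccine effect.** If R_neg = R_pos = 1, then ln R_pooled = 0 and the pooled ratio is 1 in expectation at every share.

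**Cellular responses.** A difference in pooled medians is not in general a weighted average of the two serogroup differences, so the formula does not carry over. The protocol gives nothing from which to size this effect.

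**The case against.** A reader might infer that the pooled fold-rise ratio reflects recruitment instead of the vaccine. The documents do not support that. Allocation is 2:1 by randomisation, so the pooled log ratio is in expectation a weighted average of two randomised vaccine-versus-placebo contrasts. The mix alters the size of the estimate and does not replace the vaccine effect.

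A reader might also take the rows at 25% and 50% as likely. The only documented share is 5.65%. A richer early subset is possible, because its composition is not fixed, but nothing shows that it will occur. The seropositive ratio has no source in the protocol either.

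Much is already covered. Neutralising and ELISpot results are split by serostatus in 8.5.2.2 at Weeks 6, 30 and 56, which takes in the exploratory endpoint on neutralising persistence. That duplication is untidy but loses no result. Flow cytometry is an exploratory endpoint, yet Section 6.5 leaves the decision to run such assays to the course of the trial. Section 8.3 has no formal hypothesis beyond primary efficacy in seronegative subjects, so no error rate, sample size or stopping rule is touched.

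Two possible defences carry less weight. One is that the detail belongs in a separate analysis plan, but Section 8.1 says that Section 8 is the formal plan. The other is version: the omission stands in both the 1.0USA and 2.0USA texts, and the statistical section of version 7.0 is not shown, so whether it persists there cannot be checked.

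What stands is the inconsistency itself and the missing split for ELISA binding antibody and non-ELISpot cellular measures.

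**Conclusion.** The point holds as a minor inconsistency with a real but limited effect on interpretation. As written, 8.5.9.2 reports Phase 3 binding antibody and non-ELISpot cellular responses pooled over two immunologically different groups. At the planned mix the binding ratio would be about 5% to 16% below the seronegative value. That rests on a placebo fold-rise of 1, the Phase 2 value of 23.5 carrying over, a seropositive ratio of 1 to 10, and an assayed subset that mirrors the trial. The result should not be read as a biased comparison or as a threat to any primary or secondary conclusion.

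**What to change.** In the Phase 3 part of Section 8.5.9.2, replace the stratification sentence with the one already used in 8.5.2.2: "The summaries listed above will be stratified according to disease status of the subjects and by baseline SARS-CoV-2 serostatus". This also brings the two specifications of the neutralising comparison into line. The cost is one clause. Serology is already collected at Screening and Day 0 for every Phase 3 subject, and the factor is already used throughout Section 8. At the planned share the seropositive stratum of the assayed subset would hold only about 11 or 12 subjects, so its estimates will be imprecise. The gain is a seronegative estimate that does not move with the mix.

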8.5.9.3 Concomitant Medications

Concomitant medications are those used during the course of the trial (on or after Day 0). Partial stop dates of concomitant medications will be assumed to be the latest possible date consistent with the partial date; start dates will not be imputed. Data for all concomitant medications will be summarized with percentages by treatment arm, for the ITT and PP populations. These summaries will be performed according to Phase. For the Phase 3 segment, the analyses listed above will also be performed according to SARS-CoV-2 serostatus at baseline.

8.6 SAMPLE SIZE/POWER

Phase 3 segment: The trial is case-driven. A total of 149 observed cases among baseline SARS-CoV-2 seronegative subjects will be required to provide 90% power to declare the vaccine efficacious (>30%), assuming a true efficacy of 60% and utilizing the methodology

INO-4800	COVID19-311
Inovio Pharmaceuticals, Inc.	Clinical Protocol

described in Section 8.5.1 and Section 8.5.6. A sample size of 6714 baseline SARS-CoV-2 seronegative subjects will be required to achieve this number of cases assuming an underlying attack rate of 3.7%.

8.7 **RANDOMIZATION AND BLINDING**

Phase 2 Segment

Subjects will be randomized (3 INO-4800 1.0 mg, one injection: 3 INO-4800 2.0 mg, two injections:1 Placebo, one injection: 1 Placebo, two injections).

The study is blinded. It is double-blinded within dose group. Randomization and blinding will avoid bias in the assignment of subjects to treatment, increase the likelihood that known and unknown subject attributes (e.g., demographics and other baseline characteristics) are evenly balanced between treatment groups, and enable valid statistical comparisons between treatment groups. Subject treatment assignments will be unblinded after Phase 2 subjects have reached the Week 30 visit.

Phase 3 Segment

Subjects will be randomized (2 INO-4800:1 Placebo). Randomization will be stratified according to two factors, each with two levels: a) age-group age category (18-50 years vs. ≥51 years) on Day 0, and b) presence or absence on Day 0 of underlying medical conditions that increase risk of severe COVID-19 disease, per US CDC criteria.

The study is double-blinded. Randomization and blinding will avoid bias in the assignment of subjects to treatment, increase the likelihood that known and unknown subject attributes (e.g., demographics and other baseline characteristics) are evenly balanced between treatment groups, and enable valid statistical comparisons between treatment groups.

9.0 **ETHICS**

9.1 INVESTIGATOR AND SPONSOR RESPONSIBILITIES

The Investigator and Sponsor are responsible for ensuring that the clinical trial is performed in accordance with the protocol, the principles of the Declaration of Helsinki, Good Clinical Practice (GCP) and applicable regulatory requirements.

9.2 INSTITUTIONAL REVIEW BOARD (IRB)/RESEARCH ETHICS BOARD (REB)/ETHICS COMMITTEE (EC)

The Investigator will commence the clinical trial after full approval of the protocol and adjunctive materials (e.g., ICF, advertising) has been obtained from the applicable IRB/REB/EC and a copy of IRB/REB/EC approval documentation has been received by the Sponsor.

Investigator responsibilities relevant to the IRB/REB/EC include the following:

- Submit continuing review reports to the IRB/REB/EC as required, and request rereview and approval of the clinical trial at least once a year during the conduct of the clinical trial;
- Notify the Sponsor immediately of any suspected unexpected adverse drug or device events/effects;
- Notify the IRB/REB/EC immediately if the Sponsor notifies the Investigator about any reportable safety events;

INO-4800	COVID19-311
Inovio Pharmaceuticals, Inc.	Clinical Protocol

- Obtain approval from the IRB/REB/EC for protocol amendments and for revisions to the consent form or subject recruitment advertisements, as required;
- Submit reports on, and reviews of, the clinical trial and its progress to the IRB/REB/EC at intervals stipulated in their guidelines and in accordance with pertinent regulations and guidelines;
- Maintain a file of clinical trial-related information (refer to clinical trial files) that includes all correspondence with the IRB/REB/EC;
- Notify the IRB/REB/EC when the clinical trial is completed (i.e., after the last clinical trial visit of the final clinical trial subject);
- After clinical trial completion (within three [3] months is recommended), provide the IRB/REB/EC with a final report on the clinical trial.

Institutional Biosafety Committee (IBC)

The Investigator will undertake the trial after full approval of the protocol and adjunctive materials (e.g., pharmacy manual) has been obtained from the applicable IBC and a copy of this approval has been received by the Sponsor.

Investigator responsibilities relevant to the IBC include the following:

- Notify the Sponsor, IBC and NIH OSP within 30 days of any:
 - Substantial problems or violation of the NIH Guidelines
 - Significant research related accidents or illnesses
- Notify the IBC to any changes to the research (dosage, procedure, etc.) or facility (new space, remodeling, etc.).

9.3 **PROTECTION OF HUMAN SUBJECTS**

